### **4.2 Inclusion Criteria**

- Patients > 18 years of age
- Present for management of AF
- ICM is inserted at the discretion of the treating physician

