### **1.2 Secondary Objectives**

- To evaluate differences in catheter ablation (CA) and AAD for rhythm control and AF-related complications in those with and without ICM.

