## **3 STUDY DESIGN**

We propose a multi-center, retrospective study to evaluate the use of ICM versus traditional, non-ICM methods such as ECGs, Holter, and mobile cardiac outpatient telemetry (MCOT) units, referred to as non-ICM from here on out, from 2018 to 2021. The primary outcome will be the evaluation of AF freedom at 12 months with continued AAD and OAC use. Secondary outcomes are described above. This study will be approved by the Institutional Review Board (IRB), and patient consent will not be required due to the nature of the study.

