## **4 SELECTION AND ENROLLMENT OF PARTICIPANTS**

### **4.1 Study Enrollment Procedures**

#### **4.1.1 Screening**

Patients will be identified for screening via diagnosis codes for AF on chart review. This can be easily identified by querying current electronic medical record systems. If needed, patients with ICMs can be identified by lists maintained at each study center of those who undergo ICM insertion.

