### **4.3 Exclusion Criteria**

- Patients < 18 years of age
- Presence of a permanent pacemaker, implantable cardiac defibrillator, or cardiac resynchronization therapy
- Unable to tolerate ICM or traditional monitoring with ECG, Holter, or MCOT monitoring
- Unable to tolerate AAD, OAC, and CA as part of AF standard of care
- ICM inserted for cryptogenic stroke or syncope
- Was not followed > 12 months
- CA performed for AF before ICM implant

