## 6 STUDY PROCEDURES

### 6.1 Description of Evaluation

*Table 1. Variables for data collection will include but are not limited to the following.*

Variables	Description and Definition
Age	## Years
Gender	0 = Male, 1 = Female
BMI	## kg/m2
Race	0 = Caucasian, 1 = African American, 2 = Hispanic, 3 = Asian, 4 = Other
Hypertension	0 = No, 1 = Yes
Hyperlipidemia	0 = No, 1 = Yes
Diabetes Mellitus	0 = No, 1 = Yes
Coronary Artery Disease	0 = No, 1 = Yes
CVA/TIA	0 = No, 1 = Yes
Peripheral Artery Disease	0 = No, 1 = Yes
Obstructive Sleep Apnea	0 = No, 1 = Yes
Compensated HF (EF > 35%)	0 = No, 1 = Yes
History of Smoking	0 = No, 1 = Yes
Thyroid Dysfunction	0 = None, 1 = Hypothyroidism, 2 = Hyperthyroidism
Chronic Obstructive Pulmonary Disease	0 = No, 1 = Yes
Gastrointestinal Disorders	0 = No, 1 = Yes
CHADS 2 /VASC 2 Score	##
Antiarrhythmic Drug	
History of Cardioversion	0 = No, 1 = Yes
Baseline AAD Use	0 = No, 1 = Yes
Duration of Arrhythmia	## Mos.
Left Atrial Size	## cm.
Left Ventricular Ejection Fraction	## %
Access to EP	0 = No, 1 = Yes
Compliance to OAC	0 = No, 1 = Yes
Attempted AAD	0 = No, 1 = Yes
Need for Catheter Ablation	0 = No, 1 = Yes
Time to Catheter Ablation	## Days
Number of Monitors used Post-CA	##

Type of Monitors Used	0 = MCOT, 1 = 48-Hr Holter
Need for Redo Ablation	0 = No, 1 = Yes
Time to Redo Ablation	## Days
CV-Related Hospital Duration	## Days
Length of Stay	## Days
AF-Related Hospitalization	0 = No, 1 = Yes
HF-Related Hospitalization	0 = No, 1 = Yes
Bleeding Complication	0 = No, 1 = Yes
Stroke and TIA	0 = No, 1 = Yes
Freedom of AF at 12 Mos.	0 = No, 1 = Yes
Continued OAC Use	0 = No, 1 = Yes
Continued AAD Use	0 = No, 1 = Yes

Abbreviations: BMI – body mass index, CVA = cerebrovascular accident, TIA – transient ischemic attack, AAD = antiarrhythmic drug, CV – cardiovascular, CA = catheter ablation, AF – atrial fibrillation, HF – heart failure, OAC – oral anticoagulation, MCOT – mobile cardiac outpatient telemetry

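### Entry admits permanent AF, Table 1 has no AF type and no adjustment is planned, so an imbalance in AF type between arms would distort the rhythm outcomes in a direction the documents do not settle

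*Combined protocol and SAP*

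**What the plan says.** - **Screening (4.1.1):** "Patients will be identified for screening via diagnosis codes for AF on chart review". Lists of ICM recipients may be used as well, if needed.
- **Inclusion (4.2):** adults who "Present for management of AF". The same list states that "ICM is inserted at the discretion of the treating physician".
- **Exclusions (4.3):** none concerns AF type, permanent AF or a rate-control strategy. The nearest is "Unable to tolerate AAD, OAC, and CA as part of AF standard of care".
- **Outcomes:** section 3 states: "The primary outcome will be the evaluation of AF freedom at 12 months with continued AAD and OAC use". Section 5.1 repeats AF freedom as primary. Section 9.3 lists time of AAD initiation, time to CA, arrhythmia recurrence and redo ablation as primary. The secondary objective (1.2) is "To evaluate differences in catheter ablation (CA) and AAD for rhythm control and AF-related complications in those with and without ICM".
- **Data (6.1, Table 1):** the fields include "Duration of Arrhythmia", left atrial size, history of cardioversion, baseline AAD use and attempted AAD. AF type is not among them. The caption leaves the list open: "Variables for data collection will include but are not limited to the following".
- **Analysis (9.4):** t-tests, Mann-Whitney, Chi-square and Cox models at p < 0.05. No covariates, matching, weighting or stratification are named.

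**The concern.** The rhythm outcomes suit patients in whom sinus rhythm is being sought; the entry criteria do not require that. By permanent AF I mean AF accepted as continuous and managed without any attempt at rhythm control. Such a patient has a fixed result on several outcomes whatever the monitor: not free of AF at 12 months, no AAD started for rhythm control, no ablation and no redo ablation. Recurrence is undefined, because there is no AF-free period to recur from.

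If the two arms held equal shares of these patients, the effect would be mainly dilution. The arms are formed by physician choice, however, and AF type may influence that choice. Section 2.1 describes the ICM as a means of assessing AF burden and therapy efficacy, which offers less when AF is already known to be continuous. It is therefore plausible, though not documented, that permanent AF would be commoner in the non-ICM arm. With no AF-type field and no adjustment planned, a case-mix difference could be reported as an effect of monitoring.

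**Working it through.** **The plan's own figure.** Section 9.2 states 99% power with 2500 patients. It cannot be reproduced, because no AF-freedom rates or effect size are given; the only stated assumption is equal AAD, OAC and CA use rates. For scale, 1250 per arm (two-sided 0.05, pooled variance) has 99% power for a true difference of about 8.5 points from a base of 50%, and about 6.4 points from a base of 80%.

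**Inputs**
- From the documents: n = 1250 per arm (4.1.2, 9.2) and significance at p < 0.05 (9.4). Two-sided testing is stated for t-tests and assumed here for Chi-square.
- Assumed, because the documents give no figures: AF freedom p = 0.60 in non-permanent patients in both arms (no true ICM effect), 0 in permanent AF, 2% permanent AF in the ICM arm, and equal AF detection in both arms.

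**Formulas**
- Observed freedom in an arm = p × (1 − s), where s is the share in permanent AF.
- z = (difference) / √[2 × p̄(1 − p̄)/1250], where p̄ is the mean of the two observed proportions.
- The chance of significance is the usual normal-approximation power for two proportions.

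**Results.** ICM arm: 0.60 × 0.98 = 58.8%.

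| s, non-ICM | Non-ICM freedom | False gap | z | Chance of false ICM benefit |
|---|---|---|---|---|
| 5% | 0.60 × 0.95 = 57.0% | 1.8 points | 0.91 | about 15% |
| 10% | 0.60 × 0.90 = 54.0% | 4.8 points | 2.42 | about 68% |
| 20% | 0.60 × 0.80 = 48.0% | 10.8 points | 5.41 | over 99% |

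**Sensitivity to p.** For 2% v 10%, the chance runs from 52% at p = 0.50 to 96% at p = 0.80.

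**Sensitivity to direction.** Exchange the shares (10% permanent in ICM, 2% in non-ICM) and the result is 54.0% v 58.8%, with the same 68% chance, now of a false ICM harm.

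**Sensitivity to detection.** Suppose ICM finds every recurrence and non-ICM monitoring misses a fraction m of recurrences in non-permanent patients. Observed non-ICM freedom becomes (1 − s)(0.60 + 0.40m). Setting this to 0.588 gives the m that cancels the gap: m = [0.588/(1 − s) − 0.60]/0.40.
- s = 5%: m = 4.7%
- s = 10%: m = 13.3%
- s = 20%: m = 33.75%

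Section 2.1 cites a threefold rise in AF detection with ICMs. Read literally as m = 2/3, freedom in non-permanent non-ICM patients is 0.60 + 0.40 × 2/3 = 86.7%. The arm then shows 82.3%, 78.0% or 69.3% for s = 5%, 10% or 20%, all above 58.8%, so the net gap is against ICM. That figure is cited for cryptogenic stroke, syncope and post-ablation patients, and 4.3 excludes ICMs placed for the first two reasons, so how far it carries over is unknown.

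**Other outcomes.** The sign need not agree across outcomes. Extra permanent AF in the non-ICM arm lowers AF freedom there, but it also lowers redo ablation there and delays or removes first ablation and AAD initiation.

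**The case against.** The strongest objection is to any claim about direction. A reader might infer that the plan will produce a false ICM benefit. The documents do not support that: nothing states that ICMs are seldom placed in permanent AF, the reverse imbalance would produce a false harm, and the detection difference in 2.1 pushes AF freedom against ICM and could cancel or reverse the gap. This stands. It does not remove the problem, because two biases of unknown size cannot be relied on to cancel.

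A reader might also infer that the non-ICM arm comes from a different source. Section 4.1.1 screens all patients by AF codes, with ICM lists only as a supplement, so unequal loading rests on physician selection alone.

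It would also be too strong to say that no adjustment could help. The Table 1 list is open, and cardioversion history, baseline and attempted AAD, arrhythmia duration and left atrial size are partial proxies. None identifies permanent AF, however; nothing commits sites to collect AF type; and 9.4 plans no adjustment with any of them.

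The tolerance exclusion in 4.3 may remove a few such patients. It concerns ability to take treatment, not the strategy chosen, so a rate-controlled patient who could tolerate these treatments still qualifies.

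Finally, broad entry fits the aim in 2.2 of addressing all AF patients. That is a reason to keep permanent AF for the outcomes where it is informative, not for AF freedom.

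**Conclusion.** The gap is real: entry allows permanent AF, AF type is not a listed variable, arms are formed by physician choice, and no adjustment is planned. Any imbalance in permanent AF would distort AF freedom, arrhythmia recurrence, time to CA, AAD initiation and redo ablation independently of the monitor. The direction is not documented.

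The size depends wholly on assumed shares and rates. Under the stated assumptions, including equal detection, an imbalance of 3 percentage points matters little (about 15% chance of a false result), while one of 8 points gives about 68%. The resulting 4.8-point gap is somewhat below the 6.4 to 8.5 points for which the study has 99% power. Because the shares are unknown and the net bias could run either way, this is a point that should be fixed rather than a demonstrated false result.

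**What to change.** 1. **Table 1:** add AF type at enrollment (paroxysmal / persistent / permanent or rate control only). Define the enrollment date the same way in both arms; no such definition is given now, and 9.1 allows crossover to ICM at any time. Take AF type from what the chart showed at that date, so that later ICM recordings do not reclassify one arm only.
2. **Sections 3, 5.1 and 9.3:** analyse AF freedom, arrhythmia recurrence, time to CA, AAD initiation and redo ablation only in patients not in permanent AF at that date, by one rule for both arms.
3. **Section 9.4:** include AF type as a covariate in the Cox models. The new field changes nothing unless the restriction and the adjustment are written into the analysis.
4. **Keep permanent-AF patients** for OAC, thromboembolic, bleeding, hospitalization and mortality outcomes, which preserves the aim in 2.2.

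This does not address the detection difference, which needs its own handling.

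**Cost:** one more chart field, a few sentences, and a somewhat smaller evaluable number for the rhythm outcomes. At the illustrative shares of 2% and 10%, 1250 × 0.98 = 1225 and 1250 × 0.90 = 1125 patients would remain. The field is cheap to add before chart abstraction; adding it afterwards would mean reopening about 2500 charts.

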## 5.2 Handling of Study Interventions

Screening, enrollment, and data collection will be performed by the Electrophysiology team and Kansas City Heart Rhythm Research Foundation (KCHRRF) members or respective institutions. Once data is collected, it will be analyzed by KCHRRF staff.

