## 9.3 Outcomes

Primary	Secondary

• Access to care

• Time of AAD initiation

• Time of OAC initiation

• Time to CA

• Any changes or discontinuation of AAD post-ablation

• Any changes or discontinuation of OAC post-ablation

• Arrhythmia recurrence

• Redo Ablation

	

• Systemic thromboembolic events

• All AF and cardiovascular related hospitalization

• Heart failure exacerbations

• Bleeding complications

• Cardiovascular mortality

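### Neither arm has to be under electrophysiology care and no analysis accounts for it, so unequal access could pass for an ICM effect on ablation and antiarrhythmic drug outcomes

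*Combined protocol and SAP*

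**What the plan says.** Section 3 sets the question as a contrast of monitoring methods, to "evaluate the use of ICM versus traditional, non-ICM methods such as ECGs, Holter, and mobile cardiac outpatient telemetry (MCOT) units".

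The population is built as follows.

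- **Screening (4.1.1).** "Patients will be identified for screening via diagnosis codes for AF on chart review". For one arm there is a further source: "patients with ICMs can be identified by lists maintained at each study center of those who undergo ICM insertion".
- **Inclusion (4.2).** Adults who "Present for management of AF". Exposure arises because "ICM is inserted at the discretion of the treating physician"; that physician's specialty is not stated.
- **Exclusion (4.3).** There are rules on existing cardiac devices, tolerance of monitoring and treatment, ICM indication, length of follow-up and prior ablation. None concerns EP care.
- **Who enrolls (5.2).** "Screening, enrollment, and data collection will be performed by the Electrophysiology team" and research foundation members, or by the respective institutions.

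Table 1 in section 6.1 has a field "Access to EP 0 = No, 1 = Yes", with no time point. Section 9.3 lists "Access to care" as a primary outcome, together with time to AAD initiation, time to CA, AAD changes after ablation, and redo ablation. Section 9.4 plans t-tests, Mann-Whitney tests, chi-square tests and Cox models. It names no covariates, matching, propensity score, stratification or restriction.

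**The concern.** Ablation and redo ablation depend on reaching an electrophysiologist, and AAD management plausibly does so in part. A patient with no route to EP care will have few or late events of this kind whichever monitor was used. If such patients are more common among the controls, the ICM arm will show earlier and more frequent ablation and drug treatment even if the device changes nothing.

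The plan has no step that would prevent or reveal this. Eligibility does not equalize access, allocation is not randomized, and the planned tests are unadjusted as written. A positive result could then be read as support for the section 2.2 hypothesis that ICMs should be used in all patients with AF, when part or all of it reflects who was already in specialist care.

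**Working it through.** **The plan's own figures.** The protocol gives no rate of EP access and no CA rate, so there is no stated figure on this point to reproduce. The 99% power in section 9.2 comes with no effect size. Its only stated assumption is no difference in treatment use, under which a two-sided 0.05 test rejects 5% of the time. That figure is not used below.

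**Inputs from the protocol.** 1250 patients per arm (9.2) and significance at 0.05 (9.4), taken as two-sided.

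**Assumed inputs (not in the documents).**

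- s = share without EP access in the non-ICM arm minus that share in the ICM arm. For simplicity the ICM share is set to zero, so s is the control share.
- c = 12-month CA rate with access, the same in both arms (no ICM effect).
- r = 12-month CA rate without access.

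**Formula.** The control rate is (1 − s)c + s·r, so the false difference is c − [(1 − s)c + s·r] = s × (c − r).

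**One case in full.** With s = 0.10, c = 0.40 and r = 0.10:

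- Control rate = 0.90 × 0.40 + 0.10 × 0.10 = 0.37.
- False difference = 0.40 − 0.37 = 0.03, or 3 points.
- Standard error = √[(0.40 × 0.60 + 0.37 × 0.63)/1250] ≈ 0.0195.
- Probability of rejection ≈ P(Z > 1.96 − 0.03/0.0195) ≈ P(Z > 0.42) ≈ 0.34.

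**Range, all with c = 40% and no true ICM effect.**

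| Controls without access (s) | CA without access (r) | False difference (points) | Chance of p < 0.05 |
|---|---|---|---|
| 0% | any | 0 | 5% |
| 2% | 10% | 0.6 | 6% |
| 10% | 30% | 1.0 | 8% |
| 5% | 10% | 1.5 | 12% |
| 20% | 30% | 2.0 | 18% |
| 10% | 10% | 3.0 | 34% |
| 20% | 20% | 4.0 | 54% |
| 10% | 0% | 4.0 | 54% |
| 20% | 10% | 6.0 | 87% |
| 20% | 0% | 8.0 | 99% |

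If some ICM patients also lack access, s is the difference between the two shares and the bias shrinks accordingly.

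**Can adjustment deal with it?** Suppose every ICM patient has access. Patients without access are then all controls, and in a model with an access term they inform only that term. The ICM coefficient comes from patients with access, which is the same contrast that restriction gives. In a simulation of the s = 10% and s = 20% cases (CA 40% v 10%, no ICM effect, 1000 runs of a linear model), unadjusted rejection was 33% and 86%. With an access term it was about 6% in both.

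**The case against.** The strongest reply is that the imbalance may be small. A diagnosis code only starts screening: controls must also present for AF management, pass the tolerance exclusions and have more than 12 months of follow-up. The EP team does part of the enrolling. The 0/1 coding of EP access is the format of nearly every binary field in Table 1, so it shows that patients without access are permitted, not that many are expected. This all stands, and it is why the table starts at negligible values. It does not remove the problem, because the protocol neither bounds the share nor plans an analysis that would be sound if the share were large.

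A reader might infer more than the documents support, in three ways.

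- **That ICM patients have EP access by definition, so the study really compares specialist with non-specialist care.** Section 4.2 says only that a treating physician decides, and section 6.3 gives both arms a treating physician. Access would replace the monitoring contrast only if no control had it. In every scenario above, at least 80% of controls do.
- **That only restriction can help.** The last step of the working shows that a baseline access term gives the same contrast when few or no ICM patients lack access.
- **That every comparison should be filtered on the existing Table 1 field.** The field has no date, and access to care is itself a primary outcome. If the field records access gained during follow-up, filtering on it would condition on something that monitoring may have changed, and would remove a listed outcome.

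**Conclusion.** The point holds as a risk of confounding that the plan leaves open. It applies to time to CA, redo ablation, and AAD initiation or changes. Without an EP criterion or any stated adjustment, a difference in access between arms would carry straight into those results.

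Its size cannot be determined from the protocol. Under the assumptions above it runs from negligible (0.6 points, about 6% rejection) to decisive (8 points, 99%), and 3 points with 34% rejection at an intermediate setting. These figures rest on assumed CA rates, an ICM arm with full access and no true device effect. Because the correction is cheap and the result could be misleading without it, the change should be made before the data are analyzed.

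**What to change.** 1. Define an index date that applies to both arms.
2. Record from the chart whether the patient was under EP care at or before that date. Keep this baseline item separate from any access gained during follow-up.
3. For time to CA, redo ablation and the AAD outcomes, make the primary analysis the ICM v non-ICM comparison among patients under EP care at the index date. Where few ICM patients lack access, including baseline EP care as a covariate in the Cox model is equivalent. State in section 9.4 which of the two is used.
4. Report the unrestricted comparison of those outcomes as a sensitivity analysis, with the share under EP care at the index date in each arm.
5. Keep access to care as an outcome in the full population, and do not filter any analysis on access measured after the index date.

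The cost is one dated chart item per patient and a short addition to section 9.4. Under the restricted analysis, results for those outcomes would apply to EP-managed patients only, and the number analyzed would fall by however many patients lack baseline EP care.

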### **4.3 Exclusion Criteria**

- Patients < 18 years of age
- Presence of a permanent pacemaker, implantable cardiac defibrillator, or cardiac resynchronization therapy
- Unable to tolerate ICM or traditional monitoring with ECG, Holter, or MCOT monitoring
- Unable to tolerate AAD, OAC, and CA as part of AF standard of care
- ICM inserted for cryptogenic stroke or syncope
- Was not followed > 12 months
- CA performed for AF before ICM implant

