## **5 STUDY INTERVENTIONS**

### **5.1 Interventions, Administration, and Duration**

No intervention or administration will be performed due to the observational nature of each phase. Charts of patients enrolled in the study will be reviewed for an initial monitoring method, any changes in

management, including AAD, OAC, CA, as per physicians' preference, arrhythmia recurrence, need for redo CA, and AF-related complication, for 12 months after enrollment. Lastly, the primary outcomes of AF freedom and continued AAD and OAC use will be noted at the end of the study duration.

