## 7 SAFETY ASSESSMENTS

There are no safety concerns for this study. Adverse AF, AAD, OAC, and ICM insertion events will be noted as outcomes.

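### The two tolerance exclusions have no time point, so a retrospective chart review can drop patients for intolerance arising in follow-up that the study counts as an outcome, possibly to a different extent in each arm

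*Combined protocol and SAP*

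**What the plan says.** Section 4.3 has two tolerance exclusions. One covers monitoring: "Unable to tolerate ICM or traditional monitoring with ECG, Holter, or MCOT monitoring". The other covers treatment: "Unable to tolerate AAD, OAC, and CA as part of AF standard of care". Neither is defined or given a time point. The same list also excludes anyone who "Was not followed > 12 months", a criterion that can be applied only by looking at the follow-up.

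Section 3 sets the design: "We propose a multi-center, retrospective study to evaluate the use of ICM versus traditional, non-ICM methods". Patients are found by diagnosis code on chart review (Section 4.1.1) and enrolled once they meet the criteria (Section 4.1.2).

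The outcomes overlap with intolerance in several places:

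- Section 7: "Adverse AF, AAD, OAC, and ICM insertion events will be noted as outcomes".
- Section 5.1: "the primary outcomes of AF freedom and continued AAD and OAC use will be noted at the end of the study duration".
- Section 9.3, primary list: "Any changes or discontinuation of AAD post-ablation" and "Any changes or discontinuation of OAC post-ablation".
- Section 9.3, secondary list: bleeding complications.

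Section 9.1 lets patients who start on traditional monitoring move to the ICM group at any time.

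**The concern.** In a prospective trial one could presume that a tolerance criterion is judged at baseline. Here the person screening the chart can see the whole course. A patient who bled on OAC and stopped it in month four is an outcome event under Sections 5.1 and 9.3. If the second bullet is taken to cover intolerance of OAC alone, the same patient may also be ineligible under Section 4.3, and the plan does not say which rule prevails.

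Excluding on events after the start of follow-up selects patients on the outcome. Two things are at stake. Rates of discontinuation, bleeding and device events can be understated. The comparison between arms can also be distorted if the arms lose patients to different extents or of different kinds. Centers may read the bullets differently, since screening is done locally and no abstraction rule is given.

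**Working it through.** **Plan's own figure.** The only computed design figure is 99% power with 1250 per arm (Section 9.2). It cannot be reproduced, because no event rate or effect size is given. This point does not depend on it.

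**Step 1: is intolerance confined to baseline?** Section 4.3 gives no date. Section 5.1 counts 12 months from enrollment, but enrollment follows the chart screen, so it does not mark a clinical starting point. No index date is defined for either arm. The follow-up criterion in the same list already uses later information. The text therefore allows both a baseline-only reading and a whole-chart reading.

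**Step 2: whom can each clause reach?**

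| Clause | Patients it can reach | Counted outcomes it overlaps |
|---|---|---|
| Intolerance of ICM | Essentially those implanted, including crossovers | ICM insertion events |
| Intolerance of ECG, Holter or MCOT | Users of these methods, including the non-ICM arm | None named in Section 7 |
| Intolerance of AAD, OAC and CA | Both arms | Continued use, changes or discontinuation, bleeding, AAD and OAC adverse events |

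**Step 3: illustration for discontinuation.** All inputs are assumed. Let D be the true share who stop and f the share of stoppers excluded as intolerant. Then

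observed rate = D(1 − f)/(1 − D·f).

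- D = 20%, f = 25% (5% of the arm removed): 0.15/0.95 = 15.8%.
- D = 20%, f = 50% (10% of the arm removed): 0.10/0.90 = 11.1%.
- D = 30%, f = 25%, 50%, 75%: 24.3%, 17.6%, 9.7%.

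If D is 20% in both arms but f is 25% in one and 50% in the other, the apparent difference is 15.8 − 11.1 = 4.7 points with no true difference. If D and f are equal in both arms, the false difference is zero, although both rates are still understated. If the true rates differ, equal f shrinks the contrast: 30% v 40% gives 9.0, 7.4 or 4.6 points instead of 10 for f = 25%, 50% or 75%. Under a baseline-only reading f = 0 and nothing changes.

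These figures treat intolerance of OAC alone as excluding, which reads *and* in the second bullet as *or*. If only patients intolerant of all three treatments are excluded, f is smaller by an amount the documents do not give.

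**Step 4: illustration for the ICM clause.** Inputs are again assumed. Let P be true AF freedom, the same in both arms, q the share of the ICM arm removed, and r AF freedom in those removed. Then

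observed ICM-arm AF freedom = (P − q·r)/(1 − q).

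With P = 60%, r = 20% and 1250 analyzed per arm:

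| q | Observed | Inflation (points) | Chance of a false finding for ICM (nominal 2.5%) |
|---|---|---|---|
| 1% | 60.4% | 0.4 | 4% |
| 2% | 60.8% | 0.8 | 6% |
| 5% | 62.1% | 2.1 | 19% |
| 10% | 64.4% | 4.4 | 63% |

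If those removed fare like the rest (r = 60%), the inflation is zero for every q.

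**The case against.** The best defense is that a baseline reading is at least as natural. Patients are enrolled after screening and their charts are then reviewed for 12 months. Section 7 keeps adverse events as outcomes, and Table 1 codes continued OAC use, continued AAD use and OAC compliance as yes or no, so patients who stop are expected in the data. Under that reading no follow-up event is lost. This stands as far as it goes: a reader might infer that the exclusions necessarily delete the outcomes, and the text shows only that they can. It does not settle the matter, because the follow-up criterion in the same list looks past baseline and no index date separates the two periods.

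Four further objections stand:

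- A reader might infer that the monitoring bullet acts only in the ICM arm. Its second half covers traditional monitoring, and crossovers can be caught by the first half.
- The second bullet says *and*. Read literally, it removes only patients intolerant of all three treatments.
- Many events would still be counted: stopping for other reasons, such as physician preference, and adverse events that the patient tolerates.
- ICM insertion events have no counterpart in patients never implanted. For that outcome, a descriptive rate is understated rather than a contrast distorted. Removing those patients can still affect the other comparisons, as Step 4 shows.

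**Conclusion.** The concern holds as a defect of timing and definition. Applied as written to charts with completed follow-up, the two exclusions can select patients on events that the study counts as outcomes, and the selection may differ between arms. This is more than missing detail, because intolerance of an inserted ICM is essentially seen only after implant.

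Size and direction cannot be computed: the documents give no rate of intolerance to any monitor or treatment. It is tempting to read the 4.7-point gap as an estimate of bias. It is not one. It assumes that twice as many patients are removed from one arm as from the other, which nothing in the documents supports, and it also needs the *or* reading. It disappears with equal removal or a baseline-only rule. The wording should be corrected, but the documents do not show that the results will be biased.

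**What to change.** Amend Section 4.3 by the route in Section 4.4:

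1. Define an index date that exists for patients in both arms.
2. Restrict both tolerance exclusions to intolerance or contraindication documented on or before that date, with a stated definition applied identically in both arms.
3. Drop the ICM-intolerance clause, or limit it to a contraindication recorded before the index date.
4. State whether the second bullet means any or all of AAD, OAC and CA.
5. Keep patients who become intolerant during follow-up and record this as an outcome.

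The cost is small. The charts are the same, but abstraction needs one added item, the reason for stopping, which Table 1 does not list (the table says it is not exhaustive). Setting the index date takes some thought, particularly for non-ICM patients. Reported discontinuation and adverse event rates may be slightly higher.
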